11.3	Study Record Retention Policy	24
Section 12	PUBLICATION POLICY	25
Section 13	REFERENCES	25

Protocol Revision History

Protocol Version with Summary of Changes	Version Date

List of Abbreviations

AACO	American Association of Certified Orthoptists
AE	Adverse Event
AAFP	American Academy of Family Physicians
AAO	American Academy of Ophthalmology
AAP	American Academy of Pediatrics
AAPOS	American Association for Pediatric Ophthalmology and Strabismus
CFR	Code of Federal Regulations
CRF	Case Report Form
COC	Certificate of Confidentiality
CLIA	Clinical Laboratory Improvement Amendments
CRI	Clinical Research Institute
DCC	Data Coordinating Center
DHHS	Department of Health and Human Services
DSMB	Data Safety Monitoring Board
DSMP	Data and Safety Monitoring Plan
eCRF	Electronic Case Report Form
FWA	Federalwide Assurance
GCP	Good Clinical Practice
HIPAA	Health Insurance Portability and Accountability Act
IATA	International Air Transport Association
ICF	Informed Consent Form
IRB	Institutional Review Board
LAR	Legally Authorized Representative

MOP	Manual of Procedures
OHRP	Office for Human Research Protections
PD	Protocol Deviation
PI	Principal Investigator
QA	Quality Assurance
QC	Quality Control
RE	Reportable Event
RPM	Rotation/Revolutions per Minute
RR	Red Reflex
SAE	Serious Adverse Event
SOP	Standard Operating Procedure
SRC	Scientific Review Committee
UP	Unanticipated Problem
USPSTF	US Preventative Services Task Force

Protocol Summary

Title: *Sensitivity and Specificity of the Red Reflex Test for Detecting Anterior and Posterior Segment Ophthalmic Pathology in the Pediatric Population*

Brief Summary: *Early detection of ocular abnormalities is critical for the prevention of visual loss. The American Association for Pediatric Ophthalmology and Strabismus (AAPOS), the American Academy of Ophthalmology (AAO), and the American Association of Certified Orthoptists (AACO) continue to support inclusion of the RRT as part of the ophthalmology screening exam in the general pediatrics clinic. While there is scientific evidence demonstrating that the RRT is a fairly reliable examination technique for identifying anterior segment pathology, studies to date have highlighted significant limitations of the RRT in accurately detecting posterior segment pathology. Delayed diagnosis of such conditions can lead to significant permanent visual impairment, and in rare cases, systemic morbidity for the child.*

Aims/Objectives: *The primary aim of this study is to determine the sensitivity and specificity of the RRT performed in a pediatric ophthalmology clinic, according to standardized practice guidelines, for detecting both anterior and posterior segment pathology in the pediatric population. The secondary aim of this study is to evaluate the impact of pharmacologic dilation on the sensitivity and specificity of the RRT in detecting anterior and posterior segment pathology in the pediatric population. We hypothesize that the sensitivity and specificity of the RRT will be sufficient for detecting anterior segment pathology but will be insufficient for detecting posterior segment ophthalmologic pathology with or without pharmacologic dilation.*

Study Population: *The study population will include pediatric patients under 17 years old recruited in clinical practice with known anterior or posterior segment pathology as well as patients without anterior or posterior segment pathology. In order to determine sensitivity and*

specificity of anterior and posterior segment pathology separately, we will split the patients with pathology into two groups, anterior and posterior.

Ophthalmology residents who are blinded to the patient's ophthalmologic diagnosis (or lack thereof) will perform the standardized RRT, which includes both a lights on and lights off examination

- Study Site(s):** *Children's National Health System and Fairfax*
- Number of Participants:** *100-200*
- Accrual Ceiling:** *200. We estimate that all consented subjects will be able to participate in this routine vision exam.*
- Study Duration:** *This study is expected to be completed within one year.*
- Subject Duration:** *The subject duration is expected to be one outpatient clinic visit.*
- Objective(s):** *The primary aim of this study is to determine the sensitivity and specificity of the RRT performed in a pediatric ophthalmology clinic, according to standardized practice guidelines, for detecting both anterior and posterior segment pathology in the pediatric population. The secondary aim of this study is to evaluate the impact of pharmacologic dilation on the sensitivity and specificity of the RRT in detecting anterior and posterior segment pathology in the pediatric population. We hypothesize that the sensitivity and specificity of the RRT will be sufficient for detecting anterior segment pathology but will be insufficient for detecting posterior segment ophthalmologic pathology with or without pharmacologic dilation.*
- Methodology:** *Prospective study*
- Outcome Measures:** *Sensitivity and specificity of the RR test to detect*

anterior and posterior ocular abnormalities with and without pharmacologic pupillary dilation.

Study

Intervention/Procedures:

Ophthalmology residents who are blinded to the patient's ophthalmologic diagnosis (or lack thereof) will perform the standardized RRT, which includes both a lights on and lights off examination. Patients will then be pharmacologically dilated and the RRT repeated. Results will be recorded for each. Pharmacological dilation will be achieved according to standard practices. For all patients, one drop of proparacaine hydrochloride ophthalmic solution will be instilled in each eye to achieve anesthesia. For patients under 1 year old, one drop of Cyclomydril will then be instilled in each eye and followed second drop in each eye 5 minutes later. For children over 1 year of age, pharmacologic dilation will be achieved with 1 drop of Cyclopentolate 1% and 1 drop of Phenylephrine 2.5% in each eye. Photography may be performed to document the presence or absence of anterior and/or posterior segment pathology.

Statistical Analysis:

The baseline demographic data will be presented descriptively. Continuous data will be summarized as mean with standard deviation or median with interquartile range depending on the distribution of the data. Categorical data will be summarized using frequencies with percentage. Summary demographic statistics between patients with and without eye abnormalities will be compared using unpaired t-test (normal) and/or Mann-Whitney U test (skewed) for continuous data, and Chi-square test and/or Fisher's exact test (if any of the expected cell frequencies are <5) for categorical data. Normality assumption will be checked by using statistical test (e.g., Shapiro Wilk test) as well as graphical methods (e.g., histogram, q-q plot).

To assess our primary and secondary hypothesis, sensitivity and specificity of the red reflex test (RRT) will be determined along with their 95% confidence interval using contingency tables for both anterior and posterior segment pathology. Positive predictive value (PPV), negative predictive value (NPV), and area under ROC curve (AUC) will also be determined. We

will also compare sensitivity and specificity of RRT for both anterior and posterior pathology between with and without pharmacologic dilation using two-sided McNemar's test for correlated proportions.

All statistical tests will be two-sided and will be performed at the 5% level of significance unless otherwise stated. Stata 15.1 software will be used for all statistical analyses.

*Our sample size calculation is based on our primary hypothesis. Assuming a 75% prevalence of anterior or posterior segment pathology and a sensitivity of 90% in our sample, a total of **59** patients will be required to construct a two-sided 95% sensitivity confidence interval with a width of at most +/-10%. Under the same assumptions, the sample size needed for a two-sided 95% specificity confidence interval of +/-10% around 80% is **280**. We will take the larger one of these two, which is **280**. The power analysis was carried out using PASS 2019 software.*

Section 1: Key Roles

Principal Investigator
[name], Vice-Chair, Ophthalmology
Children's National Health System
[name]
[contact]
[contact]

Performance	Performance Site PI	Describe Activities Conducted at
--------------------	----------------------------	---

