3.1 Primary Objective(s)

The primary outcomes of this study will be the sensitivity and specificity of the RRT in detecting anterior segment pathology, as well as the sensitivity and specificity of the RRT in detecting posterior segment pathology.

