3.3 Primary Outcome Measure(s)

Number of eyes with posterior segment pathology correctly identified as having posterior segment pathology and incorrectly identified as not having pathology. Number of healthy eyes correctly identified as being healthy.

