5.1 Study Population, Recruitment and Retention

Pediatric patients will be recruited through clinical practice at the designated study sites. Participants with known anterior segment or posterior segment pathology will be eligible for inclusion. Patients who have a history of disease, treatments and/or surgical procedures affecting the ability for normal pupillary reaction are excluded. An equal number of age matched participants with a normal anterior and posterior segment exam will be recruited from routine outpatient clinic visits. Informed consent will be obtained and will include an option to be considered for medical photography. Participants may opt out of photography and still be included in the study. For Spanish speaking participants, a telephone interpreter will be used for study recruitment and informed consent. A Spanish informed consent (developed by a Spanish medical translator from our English written consent) will be provided. Current estimated number of subjects required for the study is 200 total including 100 controls. Patient charts will be accessed from date of birth to patient's current age using either Cerner or Epic depending on the study site location. Examiners will include ophthalmology residents with one completed year of ophthalmology training. They will be blinded to participants' ophthalmologic history.

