8.4 Description of Statistical Methods

To assess our primary and secondary hypothesis, sensitivity and specificity of the red reflex test (RRT) will be determined along with their 95% confidence interval using contingency tables for both anterior and posterior segment pathology. Positive predictive value (PPV), negative predictive value (NPV), and area under ROC curve (AUC) will also be determined. We will also compare sensitivity and specificity of RRT for both anterior and posterior pathology between with and without pharmacologic dilation using two-sided McNemar's test for correlated proportions.

All statistical tests will be two-sided and will be performed at the 5% level of significance unless otherwise stated. Stata 15.1 software will be used for all statistical analyses.

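### As defined, the plan yields one specificity per test condition, not separate anterior and posterior specificities, so the specificity part of the Summary hypothesis cannot be shown

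*Combined protocol and SAP*

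**What the plan says.** **Purpose of the split.** The Protocol Summary, under Study Population, aims at sensitivity and "specificity of anterior and posterior segment pathology separately, we will split the patients with pathology into two groups, anterior and posterior". No corresponding division of the unaffected children is described.

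**Controls.** Section 5.1 describes one comparison group: "An equal number of age matched participants with a normal anterior and posterior segment exam will be recruited from routine outpatient clinic visits". It gives the numbers as "Current estimated number of subjects required for the study is 200 total including 100 controls".

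**Outcome counts.** Section 3.3 covers the posterior measure and Section 3.4 the anterior measure. For the unaffected side both use the same sentence: "Number of healthy eyes correctly identified as being healthy".

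**What is to be concluded.** The Summary hypothesis is that "sensitivity and specificity of the RRT will be sufficient for detecting anterior segment pathology but will be insufficient for detecting posterior segment ophthalmologic pathology". Section 3.1 lists sensitivity and specificity for anterior disease as primary, "as well as the sensitivity and specificity of the RRT in detecting posterior segment pathology". Section 8.4 adds: "We will also compare sensitivity and specificity of RRT for both anterior and posterior pathology between with and without pharmacologic dilation", using a two-sided McNemar test.

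**Sample size.** Section 8.5 plans for one specificity, 80% with a 95% interval of +/-10%, and reaches a total of 280.

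**The concern.** Specificity is the share of unaffected eyes that the test calls normal. Dividing the affected children into anterior and posterior groups gives two sensitivities and leaves specificity as it was. The Summary therefore credits the split with something it does not deliver.

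Three things follow if the definitions are applied as they stand. One number would appear in two rows, and under Section 3.1 both rows count as primary. The specificity part of the Summary hypothesis would need that one number to be sufficient and insufficient at once. The two dilation comparisons of specificity would return the same p-value and could be mistaken for two confirmations.

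There is also a risk at the analysis stage. An analyst who wants two different specificities could get them by changing who counts as negative, and one such change would produce the predicted pattern for the wrong reason (shown in the check below).

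**Working it through.** **1. The plan's own figures (Section 8.5).** Take the smallest group whose exact (Clopper-Pearson) two-sided 95% interval has total width at most 0.20, and divide by that group's share of the sample.
- Sensitivity 90%: 44 affected; 44 / 0.75 = 58.7, rounded up to 59. This matches.
- Specificity 80%: 70 unaffected; 70 / (1 - 0.75) = 280. This matches.

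So 280 is the total needed for one specificity in one pool of 70 unaffected children. The calculation contains no second, segment-specific specificity.

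**2. Specificity under Sections 3.3, 3.4 and 5.1.** Let H be the number of healthy eyes and h the number called healthy in a given test condition.
- Posterior specificity (3.3) = h / H.
- Anterior specificity (3.4) = h / H.
- Difference = 0.

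This assumes a single normal/abnormal call and one common healthy pool.

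**3. Illustration, counted in children.** With 80 of the 100 controls called healthy, both rows read 80%, exact 95% CI 70.8% to 87.3%. With the 70 unaffected of Section 8.5, both read 80%, 68.7% to 88.6%.

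**4. Dilation tests.** McNemar's test on specificity uses the unaffected whose call changes with dilation: b from healthy to abnormal, c from abnormal to healthy. Both segments draw b and c from the same children, so the statistic and p-value are the same.

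**5. What happens if patients with other-segment disease are counted as negatives.** Assumptions, none of them in the plan except the 100 controls: 50 anterior and 50 posterior patients; 80% of controls called healthy; anterior sensitivity 90%; any abnormal call is positive.
- Posterior table: negatives are 100 controls + 50 anterior patients. Called healthy: 80 + 50 x 0.10 = 85. Specificity 85/150 = 56.7%.
- Anterior table: negatives are 100 controls + 50 posterior patients. Called healthy: 80 + 50 x (1 - posterior sensitivity).

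| Assumed posterior sensitivity | Anterior specificity | Posterior specificity |
|---|---|---|
| 4% | 128/150 = 85.3% | 56.7% |
| 10% | 125/150 = 83.3% | 56.7% |
| 30% | 115/150 = 76.7% | 56.7% |
| 50% | 105/150 = 70.0% | 56.7% |

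The false-positive rate in healthy children is 20% in every row. The gap arises because the test correctly flags anterior disease and those flags are then scored as posterior false positives.

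**The case against.** The strongest reply is that the equality depends on a scoring rule the plan leaves partly open.

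- *Segment-specific calls.* Sections 3.3 and 3.4 speak of eyes identified as having posterior, or anterior, pathology. If examiners named the segment, the same controls could give two different false-positive rates. This stands as a possibility. However, no section defines such a call, the Summary's procedures paragraph says only that results are recorded for each test, and the specificity count remains healthy eyes called healthy.
- *Other-segment patients as negatives.* A conventional two-by-two table for posterior disease could include anterior-only patients among the negatives. The plan does not say this, and its outcome sections count healthy eyes only. With an any-abnormality call, it produces the artefact shown above.
- *Fellow eyes.* The outcome counts eyes and does not expressly limit them to controls. Unaffected fellow eyes could enter, but they would separate the two specificities only if each segment's table took its own set, which the plan does not describe.
- *Limited harm.* No anterior-versus-posterior test is planned, no level is given for sufficient, and Sections 2.2 and 8.2 state hypotheses that do not predict different specificities. Section 3.4 also labels the anterior measure secondary, although 3.1 makes it primary. All of this is correct and limits the consequences, but the Summary hypothesis and Section 3.1 still rely on two specificities.

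A reader might infer that the design can never give two specificities, or that the difference is zero whatever is recorded. The documents do not support that: it follows only with a single call scored in one healthy pool, and recorded segment calls would change it.

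**Conclusion.** The plan is wrong as written on this point. With one control group normal in both segments, an identical healthy-eye count for both measures, and a single normal/abnormal call, there is one specificity per test condition. The difference between segments is zero by construction, and the two specificity McNemar tests are the same test. The Summary's statement that splitting the affected children gives separate specificities does not hold, and the specificity part of its hypothesis cannot be shown.

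A reader might go further and conclude that the study or its specificity results are invalid. That does not follow. The contrast between anterior and posterior sensitivity is unaffected, the one specificity is properly estimable in each condition, and its comparison before and after dilation remains sound.

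**What to change.** In the Summary, Sections 3.1 to 3.4 and Section 8.4:

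1. State that one specificity is estimated per test condition, from the common healthy group, and report it once. Say which eyes belong to that group.
2. Run one McNemar test of specificity with and without dilation. Keep the two tests of sensitivity, one per segment.
3. Confine the segment hypothesis to sensitivity: sufficient for anterior, insufficient for posterior.
4. State that patients with disease of the other segment are not counted as negatives for an any-abnormality call.

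Only if examiners actually record a segment-specific call should two specificities be kept. Each should then be computed from the segment-specific false-positive rate in the same controls, with the positive call for each segment defined before analysis.

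The cost is wording in the protocol and SAP, with no additional children. Unless segment calls are recorded, the sponsor gives up the claim to a segment-specific specificity.

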2.1 Background Information and Relevant Literature

The early detection of ophthalmic pathology is critical for the prevention of vision loss and systemic morbidity in rare cases. The American Academy of Pediatrics (AAP), the American Association for Pediatric Ophthalmology and Strabismus (AAPOS), the American Academy of Ophthalmology (AAO), and the American Association of Certified Orthoptists (AACO) continue to advocate for inclusion of the red reflex test (RRT) as part of the ophthalmologic screening exam in the general pediatrics clinic. However, studies to date have demonstrated that there are potential limitations to the RRT, especially in its ability to accurately and reliably detect posterior segment pathology.

Standard procedure for the RRT currently involves viewing both eyes at arms length in lighted room followed by a darkened room to assess for symmetry of the reflection in terms of brightness and color. If an abnormality is suspected, then the operator may move closer for further inspection. With its current application, the RRT introduces subjectivity in interpretation and likely variation in pupillary reflection based on factors such as, the specific lighting condition, degree of physiologic dilation, and patient movement. Differences in operator experience with the RRT may further compound the shortcomings of this exam technique. These factors unfortunately reduce the accuracy and reliability of the RRT as a screening measure.

There is ample evidence in the literature validating the RRT as a useful screening tool for pediatric anterior segment ocular pathology, with consistently high sensitivity and specificity. However, studies describing its utility in detecting posterior segment disease are lacking. Two recent studies have attempted to address this issue. Sun and colleagues used the RRT to screen over 7000 newborns followed by retinal imaging using a Retcam-3 with pharmacologic pupillary dilation. They found that for anterior segment disease, the RRT had a sensitivity of 99.6% (95% CI 97.1%-100%) compared to only 4.1% (95% CI 3.3%-5.1%, $\chi^2 = 1521.382$, $\phi = 0.836$, $P < .001$) for posterior segment pathology. In a similar study, Ludwig and colleagues detected posterior segment pathology in 49 of 194 eyes examined using the Retcam-3 with pharmacologic dilation (sensitivity = 100%); however, no abnormalities were detected in this same set of eyes with the RRT performed by a pediatrician in the newborn nursery (sensitivity = 0%).

Based on these results, there is insufficient evidence that the RRT is an effective screening exam for detecting posterior segment pathology - even with physiologic dilation during the lights off portion of the RRT. It has been established that pupillary size and viewing angle certainly do impact the quality of a posterior segment exam. In a study by Li and colleagues, the rate of tumor detection in a model eye was optimized when viewing at an oblique angle through a maximally dilated pupil of 8 mm. Even under the darkest lighting conditions, physiologic mydriasis will be limited, and especially with introduction of the direct ophthalmoscope light for the RRT. The average infant scotopic pupil size is 3.8 mm \pm 0.9 mm in diameter. When light is shone from ophthalmoscope, pupils usually constrict by 2 mm. Pharmacologic dilation, however, is not currently included as part of the practice pattern guidelines outlining the RRT due to its perceived associated potential risks and side effects.

Based on the above, additional investigation is needed to further clarify whether the sensitivity and specificity of the RRT for detecting posterior segment pathology are sufficient for its use as a screening tool, or if alternatively, this current standard practice simply offers a false sense of security. Evaluating the impact of pharmacologic dilation on the sensitivity and specificity of the RRT may help identify a potential avenue for improving the validity of the RRT as an ophthalmology screening tool.

